#### Handling of remaining intercurrent events:

- Treatment discontinuations for lack of efficacy or adverse event: consider as non-responder
- Treatment discontinuations for any other reason: set data after discontinuation to be missing

The summary measure: difference in response rates or means between ZPL389 and placebo.

Novartis	For business use only	Page 25
SAP		CZPL389A2203

As for the primary estimands, three further supportive estimands will be considered in order to investigate the effect of different methods of handling data in the cases of intercurrent events.

# 2.6.6 Efficacy over time in the presence of TCS and/or TCI use after week 16

The underlying clinical question in general is: What is the effect of the study treatment plus use of TCS and/or TCI as needed on endpoint at each week after week 16, in patients with moderate or severe atopic dermatitis, and who have received the full intended duration of treatment at that timepoint?

The secondary estimands are described by the following attributes:

**Population:** Adult moderate to severe atopic dermatitis patients as defined by the study inclusion and exclusion criteria who were randomized to treatment, and not mis-randomized in the IRT, and who had received 16 weeks of ZPL389 or placebo treatment and who entered the extension study. This implies that analyses will be based on the subset of the extension study set.

#### **Endpoints:**

IGA response at each week after week 16, where IGA response is defined as an IGA score of 0 or 1 with at least a 2 point improvement compared to baseline.

Percentage change from baseline in EASI at each week after week 16

EASI50 response at each week, where EASI50 response is defined as a reduction from baseline of  $\geq$  50% in EASI score.

EASI75 response at each week, where EASI75 response is defined as a reduction from baseline of  $\geq$  75% in EASI score.

Change from baseline in peak pruritus score at each week after week 16

**Treatment of interest:** the randomized treatment (ZPL389 or placebo) plus medications as allowed by the protocol including TCS or TCI and including rescue medication but with no further treatment for patients who discontinue study treatment due an AE or lack of efficacy.

## Handling of remaining intercurrent events:

- Treatment discontinuations for lack of efficacy or adverse event: consider as non-responder
- Treatment discontinuations for any other reason: set data after discontinuation to be missing

The summary measure: difference in response rates or means between ZPL389 and placebo.

This estimand is different to that implied in the protocol for the extension study which planned to consider patients who use rescue medication (TCS of higher potency than that included in the standardized regimen of intermittent of concomitant TCS and/or TCI use) as non-responders.

Novartis	For business use only	Page 26
SAP		CZPL389A2203

This change is justified given that the study has been stopped and detailed consideration of the impact of rescue medication use on efficacy after week 16 is no longer required.

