# 1.1 Study design

The core study (A2203) was planned as a randomized, double blind, placebo controlled, parallel group, 5-arm study in at least 360 subjects with moderate to severe Atopic Dermatitis (AD). Unbalanced randomization ratio was used, intending to result in approximately 90 subjects randomized in each of the 30 mg/day and 50 mg/day dose arms as well as in the placebo arm, and 45 subjects in each of the 3 mg/day and 10 mg/day arms. The randomization was stratified by baseline severity of atopic dermatitis (IGA score moderate or severe) and by geographical region.

The possibility to perform an interim analysis (IA) in order to support decision making concerning the current clinical study or project was addeded to the protocol in V3. This interim analysis was performed in May 2020 on 187 patients who had completed week 16 or discontinued before this timepoint. Based on the results from this IA, it was decided to stop both the core and extension studies for reasons of lack of efficacy and thus the final number of patients, and follow-up time per patient is less than planned in the protocol.

The core study (A2203) consisted of a screening period of up to 4 weeks (depending on current medication use and associated washout period), and a 16-week double blinded treatment period. The primary endpoint was to be assessed at the end of the 16 week treatment period.

After the end of treatment visit, subjects were offered the possibility of ongoing treatment in the extension study (A2203E1), or of entering the 4 week treatment-free follow up period.

[figure not shown]

The extension study (A2203E1) was intended to be a randomized, double blind, parallel group, 2-arm study in up to approximately 202 to 230 subjects. This number assumed a discontinuation rate of 15% to 25% in the core study (A2203)

In the extension study, subjects who had received ZPL389 30 mg o.d. or 50 mg o.d. doses in the core study, would continue to receive the same doses in a double-blinded fashion. Subjects who had received ZPL389 3 mg, 10 mg or placebo in the core study, would be randomized to receive ZPL389 30 mg o.d. or 50 mg o.d. in a 1:1 ratio. All subjects would receive concomitant or intermittent topical corticosteroids (TCS) and/or topical calcineurin inhibitors (TCI) along in a standardized regimen with ZPL389.

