# 2 Statistical methods

# 2.1 Data analysis general information

Novartis will perform the analyses for this study. Statistical software SAS verion 9.4 or later will be used.

All available data from the core and extension studies will be presented together.

Where summary statistics are presented these will include, for continuous variables N, mean, standard deviation, minimum, and maximum, and for discrete variables, counts and appropriate percentages.

If not otherwise specified, p-values will be presented for two-sided hypothesis testing, twosided confidence intervals will be displayed and the level of significance will be set to 5% twosided.

In general listings will be presented by treatment sequence showing the sequence of treatments in the core and extension study, i.e as follows and in this order

- Placebo did not participate in extension
- Placebo ZPL389 50mg
- Placebo ZPL389 30mg

- ZPL389 3mg did not participate in extension
- ZPL389 3mg ZPL389 30mg
- ZPL389 3mg ZPL389 50mg
- ZPL389 10mg did not participate in extension
- ZPL389 10mg ZPL389 30mg
- ZPL389 10 mg ZPL389 50mg
- ZPL389 30mg did not participate in extension
- ZPL389 30mg ZPL389 30mg
- ZPL389 50mg did not participate in extension
- ZPL389 50mg ZPL389 50mg

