#### Handling of remaining intercurrent events:

• No intercurrent events are considered.

The summary measure: difference in means between ZPL389 and placebo.

# 2.6.5 Efficacy over time up to week 16

The principles laid out for the primary estimand will be followed in calculating the summary measures for each endpoint at each time point.

The underlying clinical question in general is: What is the effect of the study treatment versus placebo on the endpoint at each week, in patients with moderate or severe atopic dermatitis, who do not use confounding therapy that may affect their AD or the assessment of it, regardless of their use of protocol-allowed concomitant medicatons, and who have received the full intended duration of treatment at that timepoint?

Other questions that may have been of interest in the case of an effective treatment, such as when is a treatment effect first seen, or how long is the treatment effect maintained for, will not be addressed.

The main secondary estimands are described by the following attributes:

**Population:** Adult moderate to severe atopic dermatitis patients as defined by the study inclusion and exclusion criteria who were randomized to treatment, and not mis-randomized in the IRT. This implies that analyses will be based on the full analysis set.

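### After Week 16 the SAP still sets ZPL389 versus placebo as the efficacy measure, although every extension entrant is on 30 or 50 mg, so the contrast is not a placebo comparison

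*SAP*

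**What the plan says.** **Design.** SAP 1.1 describes the extension as a two-arm study. For three of the five core arms: "Subjects who had received ZPL389 3 mg, 10 mg or placebo in the core study, would be randomized to receive ZPL389 30 mg o.d". The same sentence gives 50 mg as the alternative, with equal allocation. Core 30 mg and 50 mg subjects "would continue to receive the same doses in a double-blinded fashion". The treatment sequences in SAP 2.1 follow this plan; a core placebo subject who enters the extension appears, for example, under "Placebo ZPL389 50mg".

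**Estimand after Week 16.** The question in SAP 2.6.6 reads: "What is the effect of the study treatment plus use of TCS and/or TCI as needed on endpoint at each week after week 16". Its population is subjects "who had received 16 weeks of ZPL389 or placebo treatment and who entered the extension study". Its treatment attribute is "the randomized treatment (ZPL389 or placebo) plus medications as allowed by the protocol including TCS or TCI". Its measure is: "The summary measure: difference in response rates or means between ZPL389 and placebo".

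**Estimand up to Week 16.** SAP 2.6.5 uses the same sentence for its measure, but there the question is explicitly comparative: "What is the effect of the study treatment versus placebo on the endpoint at each week".

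**Methods.** SAP 2.6.7 calculates differences between dose groups and placebo for all estimands based on binary response, with no exception for 2.6.6. For continuous endpoints it takes group means at each visit but group differences at Week 16 only. Appendix 5.2.1 gives differences from placebo at every timepoint. Appendix 5.2.3 analyses the imputed response data against the placebo group.

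**The concern.** A summary measure has to compare groups that exist in the estimand's population and period. In 2.6.6 the period begins after placebo treatment has ended for everyone in the population. The SAP does not say that placebo in this section means subjects who had placebo in the core study and have since switched to ZPL389, so the label and the comparison do not match.

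Table 1-2 of the SAP marks the extension efficacy objectives for inclusion in the study report. They concern 30 mg and 50 mg given with topical treatment, with endpoints that are frequencies or changes from core baseline; none names a placebo comparator. A table of differences from placebo after Week 16 would present a comparison of ZPL389 with ZPL389 as placebo-controlled evidence. A reader could take a difference near zero as further evidence of no effect, when that contrast cannot measure the effect against placebo.

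**Working it through.** No stated sample size, power or error rate is at issue, so the check traces treatment assignment.

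**1. Who is on placebo after Week 16?** The extension sequences in SAP 2.1 are:

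| Core arm | Extension treatment | Sequences |
|---|---|---|
| Placebo | 50 mg or 30 mg | 2 |
| 3 mg | 30 mg or 50 mg | 2 |
| 10 mg | 30 mg or 50 mg | 2 |
| 30 mg | 30 mg | 1 |
| 50 mg | 50 mg | 1 |

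The total is 2 + 2 + 2 + 1 + 1 = 8. Two continue the same dose, six switch to 30 or 50 mg, and 0 of 8 have placebo after Week 16. The treatment-free follow-up does not supply a placebo group, because 2.6.6 is restricted to extension entrants.

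**2. Contrast by treatment received.** The placebo group has n = 0, so the difference cannot be estimated.

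**3. Contrast by core arm.** There are four dose-versus-placebo comparisons (3, 10, 30 and 50 mg). After Week 16 the core placebo side is a planned 1:1 mix of 30 and 50 mg.

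- Core 3 mg or 10 mg versus core placebo: the same planned mix on both sides (2 contrasts).
- Core 30 mg or 50 mg versus core placebo: one continued dose against that mix (2 contrasts).

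ZPL389 is on both sides in 4 of 4.

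**4. What the core-arm contrast measures.** Assume, for illustration only, that switched subjects reach the response rate of their new dose. With p30 and p50 as the rates on 30 and 50 mg, the core placebo side has rate (p30 + p50)/2, and the contrasts are

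- core 30 mg: p30 − (p30 + p50)/2
- core 50 mg: p50 − (p30 + p50)/2
- core 3 mg or 10 mg: (p30 + p50)/2 − (p30 + p50)/2 = 0

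No placebo rate appears in any of them. The sample size section assumes 10% on placebo and a maximum effect of 20 points, hence 30% at most on ZPL389.

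| p30, p50 | 30 mg contrast | 50 mg contrast | Effect against 10% placebo (30 mg, 50 mg) |
|---|---|---|---|
| 30%, 30% | 30 − 30 = 0 points | 30 − 30 = 0 points | 20, 20 points |
| 20%, 30% | 20 − 25 = −5 points | 30 − 25 = +5 points | 10, 20 points |

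The 20% for 30 mg in the second row is my assumption. The rows show what the contrast estimates; they do not predict results, and the interim analysis found no treatment effect.

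**5. How far the contrast reaches.** SAP 2.6.6 lists five endpoints. The three binary ones (IGA response, EASI50, EASI75) carry the placebo difference through 2.6.7. For the two continuous ones (percent change in EASI, change in peak pruritus), 2.6.7 stops at Week 16, and only 5.2.1 extends the difference to later visits.

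**6. How safety handles the same design.** For adverse events between Weeks 16 and 32, SAP 2.7.1 uses four groups: placebo or low dose followed by 30 mg, the same followed by 50 mg, continued 30 mg, and continued 50 mg. After Week 32 it uses two, 30 mg and 50 mg. Neither scheme has a placebo group. The visible SAP text gives no corresponding grouping for efficacy after Week 16.

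**The case against.** The strongest reply is that the contrast is not empty. SAP 2.2 builds the extension set from the full analysis set, which is analysed by assigned treatment. The 2.6.6 population is described by what subjects received in the core study, and the treatment attribute speaks of randomized treatment. Together these point to the core arm. This stands: a reader might infer that the analysis cannot be run at all, and the documents do not support that as the main reading. Some ambiguity remains, because core placebo, 3 mg and 10 mg subjects are randomized a second time. But the reading only makes the contrast computable; it does not make it a comparison with placebo.

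A second reply is that the useful results are already planned. SAP 2.6.7 gives response rates per group, and mean responses per visit and group with 95% confidence intervals. This also stands: a reader might infer that the extension objective cannot be answered, and that is not so. What is missing is the grouping and confidence intervals for single-group response rates.

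Third, the appendix is weak evidence of intent. The example code in 5.2.3 labels its comparison with a product that is not in this trial, so it looks like reused template text. This is fair, and is why the point rests on 2.6.6 and 2.6.7.

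A reader might also infer that the imputation has to be redesigned. The documents do not support this: 5.2.3 imputes separately by treatment group, and nothing in it calls for pooling core placebo, 3 mg and 10 mg subjects.

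Finally, the extension protocol, the table shells and some SAP sections are not among the material. The missing efficacy grouping can be asserted only of the visible text.

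**Conclusion.** The measure and the treatment attribute in SAP 2.6.6 contradict the extension design in SAP 1.1 and 2.1, and 2.6.7 carries the measure into the binary analyses. On the better-supported reading, the result is a computable contrast with the wrong name: 4 of 4 comparisons have ZPL389 on both sides. On the other reading the comparator has no subjects. The sentence shared with 2.6.5 suggests carry-over from a section where a placebo arm does exist, though the documents do not say how it arose.

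The consequence is limited. It touches secondary extension tables in an abbreviated report of a study stopped for lack of efficacy. A reader might infer that the evidence on dose-response at Week 16 is compromised; it is not, because randomized placebo treatment continues through the core treatment period and those analyses do not use 2.6.6. The conclusion needs only the assignment rules and listed sequences; it does not depend on the illustrative response rates or on how many subjects entered the extension. It merits correction because the tables are marked for the report and would be mislabelled.

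**What to change.** - **SAP 2.6.6:** state the treatment as the extension treatment, 30 or 50 mg, following ZPL389 or placebo in the core study. Replace the placebo contrast with within-group response rates and mean changes from core baseline, with 95% confidence intervals. SAP 2.6.7 already provides most of this; confidence intervals for single-group rates are the main addition.
- **SAP 2.6.7, 5.2.1 and the placebo comparison in 5.2.3:** limit differences between ZPL389 and placebo to visits up to Week 16.
- **Grouping:** state one grouping for efficacy after Week 16. Treatment sequence would serve, as would the four groups that 2.7.1 uses for Weeks 16 to 32. If the latter is chosen, note that 2.7.1 collapses to two groups after Week 32, and say what efficacy does there.
- **Any core-arm contrast after Week 16:** state beside it that both sides received ZPL389 and that dose and start time may both differ. A label such as early versus delayed start is not enough, because core 30 mg or 50 mg against switched placebo also compares one dose with a mix of two.

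The cost is wording in four SAP sections and the affected table shells and programs. It needs no new data and no change to the imputation method, and it leaves fewer comparisons than now planned.

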# 2.6.7 Statistical hypothesis, model, and method of analysis

For all estimands based on binary response rates (e.g. IGA response, EASI50 response, EASI75 response) the simple response rates for each treatment group will be calculated (i.e. number of responders (after imputation as necessary) / the number of subjects in that treatment group.

Differences in response rates between ZPL389 dose groups and placebo will be calculated, and the respective 95% confidence intervals derived using a normal approximation.

For estimands based on continuous data (e.g. percentage change from baseline in EASI, approach will be used. The model will contain treatment group, baseline EASI score, geographical region if possible, baseline IGA score, visit, baseline value\*visit and treatment group\*visit as covariates, and will use an unstructured covariance matrix. Estimates of the mean responses for each visit and treatment group, and of the differences between treatment groups at week 16 will be obtained from this model, together with 95% confience intervals.

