5.1 Treatment assignment and randomization

At Baseline, all eligible subjects will be randomized via Interactive Response Technology (IRT) to one of the treatment arms. The investigator or his/her delegate will contact the IRT after confirming that the subject is eligible according to the inclusion/exclusion criteria. The IRT will assign a randomization number to the subject, which will be used to link the subject to a treatment arm and will specify a unique medication number for the first package of study drug to be dispensed to the subject. The randomization number will not be communicated to the caller.

The randomization numbers will be generated using the following procedure to ensure that treatment assignment is unbiased and concealed from subjects and investigator staff. A subject

randomization list will be produced by the IRT provider using a validated system that automates the random assignment of subject numbers to randomization numbers. These randomization numbers are linked to the different treatment arms, which in turn are linked to medication numbers. A separate medication list will be produced by or under the responsibility of Novartis Drug Supply Management using a validated system that automates the random assignment of medication numbers to packs containing the investigational drug(s).

In the proof of concept study, response to treatment was related to the Baseline IGA score and therefore randomization will be stratified by Baseline IGA moderate (3) or severe (4). In addition, randomization will be stratified by geographical region.

The randomization scheme for subjects will be reviewed and approved by a member of the Randomization Group.

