## Handling of remaining intercurrent events:

- Treatment discontinuations for lack of efficacy or adverse event: consider as non-responder
- Treatment discontinuations for any other reason: set data after discontinuation to be missing

The summary measure: difference in response rates between ZPL389 and placebo.

This estimand differs from that intended by the protocol in that the definition of the endpoint of IGA response has changed to include any use of confounding medication as a non-response, rather than only confounding medication that was adjudicated as having an effect on the IGA response, as specified in the protocol. This change was made following the interim analysis where it was established that handling use of confounding medication did not affect the overall conclusions and so it was decided not to perform the adjudication.

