# 2.5.2 Statistical hypothesis, model, and method of analysis

The key questions to address this objective are

- Is there a dose-response relationship for IGA response after 16 weeks of treatment?
- What is the form of this dose-response?

• What doses deliver sufficient efficacy in terms of IGA response after 16 weeks of treatment?

Results from the interim analysis indicate that there is no dose-response relationship and therefore the second and third questions are no longer relevant. Thus the analysis of the primary variable will focus only on the logistic regression analysis described in the protocol, establishing the presence or absence of a dose-response relationship. The MCP-Mod procedure as outlined in the protocol will not be carried out.

The primary objective will be achieved if the null hypothesis of no difference between treatment groups is rejected at 5% one-sided level.

A logistic regression model will be fitted with IGA response as the outcome variable and treatment (dose as categorical variable) and baseline IGA as covariates.

The response  $Y_{ij}$  for subject j in dose group i receiving dose  $d_i$  is modelled as  $Y_{ij} \sim Bin(1, p_{ij})$  with  $p_{ij} = logit^{-1}(\delta_i + \mathbf{x}_{ij}; \boldsymbol{\beta}), i=1,..., 5, j=1,..., n_i$ 

where Bin(1,p) denotes the binomial distribution with parameter 1 and p,  $\delta_i$  is the effect of dose  $d_i$ ,  $\beta$  refers to the vector of regression coefficients corresponding to additional covariates  $x_{ij}$  which represent the baseline IGA category. Finally,  $n_i$  is the number of subjects allocated to each treatment group. If the covariate baseline IGA prevents fitting of a model, it will be dropped.

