## 5.2.2 Analysis of binary data

#### Risk difference and 100\*(1-α)% confidence interval

For an investigational drug group with  $n_1$  subjects at risk, independent from the control group (e.g., placebo or comparator) with  $n_0$  subjects at risk, of whom  $x_1$  and  $x_0$  experience a certain event, the risk difference is estimated as  $p_1$ - $p_0$  with  $p_1 = x_1/n_1$  and  $p_0 = x_0/n_0$ .

Exact unconditional confidence limits for the risk difference will be obtained with SAS procedure PROC FREQ and option RISKDIFF in the TABLES statement, specifying the RISKDIFF option also in the EXACT statement.

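### The primary response-rate difference is computed from crude proportions; standardising it over baseline IGA, a randomisation stratum already in the test model, would give a modestly narrower interval at almost no cost

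*SAP*

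**What the plan says.** The summary measure of the primary estimand (SAP 2.5.1) is stated as "The summary measure: difference in response rates between ZPL389 and placebo". Supportive estimands 1 to 3 use the same measure, and SAP 2.6.1 carries the approach over to EASI50 and EASI75 response.

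The SAP gives one rule for computing that difference. In 2.6.7, for all estimands based on binary response, "the simple response rates for each treatment group will be calculated"; differences from placebo follow, with "the respective 95% confidence intervals derived using a normal approximation". SAP 5.2.2 offers another interval: "Exact unconditional confidence limits for the risk difference will be obtained with SAS procedure PROC FREQ". That one is unadjusted too.

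The test is handled differently. SAP 2.5.2 fits a logistic regression with "treatment (dose as categorical variable) and baseline IGA as covariates", and states: "The primary objective will be achieved if the null hypothesis of no difference between treatment groups is rejected at 5% one-sided level".

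Protocol 5.1 gives the reason for the stratum: in the proof-of-concept study, "response to treatment was related to the Baseline IGA score and therefore randomization will be stratified by Baseline IGA". Protocol 9.4.2 averaged the per-dose logits over baseline IGA, weighting by the FAS frequencies, before MCP-Mod was applied. The SAP drops MCP-Mod and does not carry the averaging step forward.

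**The concern.** When randomisation is stratified by a prognostic factor, the design removes part of the between-patient variance from the treatment comparison. An interval built from crude proportions does not credit this, so it is wider than it need be. If the strata end up somewhat unequal across arms, the crude difference also carries that imbalance, whereas an adjusted difference does not.

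The plan already treats baseline IGA as prognostic in the stratification, in the primary test, in the imputation model (SAP 5.2.3) and in the MMRM for continuous endpoints (SAP 2.6.7). The binary rate difference, which is the stated summary measure, is the exception. At stake is a modest amount of precision, and a reported estimate that does not come from the model behind the test.

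**Working it through.** **1. The plan's own figure.** Protocol 9.8 gives 360 subjects (90:45:45:90:90) for 90% power at one-sided 2.5%, with 10% placebo response and a maximum effect of 20 points. Recomputing MCP-Mod with the seven candidate shapes, contrasts optimal for that allocation and logit-scale variances gives a minimum power of 0.914 to 0.916. The design reproduces, so 10% versus 30% with 90 per arm is a fair reference case.

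**2. Crude interval.** Var = p0(1−p0)/n + p1(1−p1)/n.
- 90 per arm: (0.09 + 0.21)/90 = 0.003333; half-width 1.96 × √0.003333 = 11.3 points.
- At the interim, 187 patients at 2:1:1:2:2 give 187 × 2/8 ≈ 47 in each larger arm: (0.09 + 0.21)/47 = 0.006383; half-width 15.7 points. The final N is not stated.

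**3. IGA-standardised interval.** With a share w of moderate patients, each arm contributes [w·pm(1−pm) + (1−w)·ps(1−ps)]/n, where pm and ps are the response rates in moderate and severe patients. The documents give neither the relation's strength nor the severe share. Both are assumed here: odds ratio (OR) 1 to 8, severe share 30% to 50%.

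Worked case, OR 4 and 40% severe:
- Placebo 10% splits into 14.05% moderate and 3.93% severe: 0.6 × 0.1405 × 0.8595 + 0.4 × 0.0393 × 0.9607 = 0.0876.
- Active 30% splits into 40.35% and 14.47%: 0.6 × 0.4035 × 0.5965 + 0.4 × 0.1447 × 0.8553 = 0.1939.
- Variance (0.0876 + 0.1939)/90 = 0.00313, which is 6.2% below 0.003333. Half-width 11.0 points.

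| Assumed OR | Variance below crude | Half-width, 90 per arm (crude 11.3) | Half-width, 47 per arm (crude 15.7) | Crude interval wider by |
|---|---|---|---|---|
| 1 | 0% | 11.3 | 15.7 | 0% |
| 2 | 1.5–2.0% | 11.2 | 15.5 | about 1% |
| 4 | 4.8–7.3% | 10.9–11.0 | 15.1–15.3 | 2–4% |
| 8 | 8.1–14.1% | 10.5–10.8 | 14.5–15.0 | 4–8% |

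With no treatment effect (10% in both arms) the variance gain over the same assumptions is 0 to 6.1%. At 90 per arm the half-width then falls from 8.8 points to no less than 8.8 × √(1 − 0.061) = 8.5.

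**4. Estimate or reported standard error?** Two-arm simulation, complete data, about 6,000 trials per setting, 90 per arm, 10% versus 25%, OR 4, 40% severe:
- Strata exactly balanced: the crude and standardised estimates both have empirical SD 0.0539. Only the mean reported SE differs, 0.0551 crude against 0.0535 standardised.
- Strata left to chance: empirical SD 0.0556 crude against 0.0542 standardised.

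**5. Residual imbalance.** The crude difference shifts by (excess severe share) × (pm − ps). Block size and number of regions are not given. Assuming blocks of 8 within region and IGA, 2 to 5 regions, 40% severe and a stop at 187 patients, the median imbalance against placebo is 1.3 to 2.5 points. With pm − ps of 10 to 30 points, the shift is 0.10 × 1.3 ≈ 0.1 to 0.30 × 2.5 ≈ 0.8 points.

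**6. Test against interval.** Same simulation at the SAP's own levels (5% one-sided test, 95% two-sided interval): the two disagree in 7–10% of trials with the crude difference and in 6.5–7.5% with the standardised one. At 47 per arm the figures are 10–13% and 9–10%.

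**The case against.** The strongest reply is that adjusted primary results are already planned. SAP 2.5.3 links estimation of the Week 16 rates to the logistic regression, the code in SAP 5.2.2 requests model-based response probabilities, and SAP 5.2.3 pools odds ratios. The rule for simple rates sits under secondary objectives, and Protocol 9.5.1 also planned secondary rate differences with a normal approximation and no named covariate. This shows that only the rate difference is unadjusted. It does not supply an adjusted one: an odds ratio is not the stated summary measure, no text turns the model-based probabilities into a difference with an interval, and 2.6.7 covers all binary estimands and names IGA response.

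The second reply is that the loss is small. That stands. Under stratified randomisation it is mainly a slightly conservative standard error, and a weak relation makes it negligible.

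A reader might infer three stronger things, none supported:
- That the crude difference is biased. It is not; it estimates the stated summary measure without bias.
- That early stopping left severity badly unbalanced, say by 10 points, which would move the difference by 1 to 3 points. The documents do not mention blocks, so incomplete blocks are an inference. Under the blocked scheme assumed above, such an imbalance with 50 mg never occurred in 3,000 simulated trials; with 10 mg it occurred in none with two or three regions and in about 1% with five.
- That omitting baseline IGA is why test and interval can conflict. Most of the conflict comes from the differing levels and from the odds-ratio versus difference scale.

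**Conclusion.** The point holds as a modest, inexpensive improvement. The primary, supportive and EASI50/75 rate differences ignore a stratification factor that the protocol ties to response and that the primary test uses. The cost is an interval wider by about 1% at an odds ratio of 2, 2 to 4% at 4 and 4 to 8% at 8, and nothing if there is no relation. These figures are for 10% versus 30% response and a severe share of 30% to 50%. Odds ratio and severe share are assumptions, and with no treatment effect the loss is smaller. The trial stopped for lack of efficacy, and a slightly conservative interval is unlikely to alter that conclusion.

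**What to change.** For the core-study comparisons with placebo, state in SAP 2.5.2 and 2.6.7 that within each imputed data set:
- the logistic model of SAP 2.5.2 is fitted, with the corresponding model for EASI50 and EASI75;
- each arm's response probability is averaged over the FAS baseline IGA distribution;
- the difference from placebo is taken, with a delta-method standard error.

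Pool the differences by Rubin's rules. If too few responders prevent the model from fitting, use a Mantel-Haenszel difference by baseline IGA instead of falling back to the crude one. Keep the simple rates as descriptive columns.

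The cost is a few lines of code and no new data. Two neighbouring matters need their own edit, because this change does not settle them: the 5% one-sided test beside a 95% two-sided interval, and the choice between the interval methods in SAP 2.6.7 and 5.2.2.
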